Since 2010, the CLSA team has achieved major successes in the design and implementation of the CLSA, from building infrastructure to capture, manage, and store data and bio-samples, assembling measurement tools and conducting pilot work to assess the feasibility of numerous aspects of the study to reaching our pre-established recruitment target of 50,000 participants by the spring of 2015. We have met our recruitment and baseline data collection goals for the CLSA Tracking (20,000) and have started the Maintaining Contact Questionnaire (MCQ, the between-wave brief questionnaire) with these participants. At the time of writing, 4,000 participants have completed the MCO with a retention rate of approximately 95% (4% have refused to continue and 1% have died). We are also meeting our goals for recruiting the 30,000 CLSA Comprehensive participants. As of June 10th, 2014, we have completed recruitment, consent, and baseline face-to-face interviews with 22,000 people, about 20,000 of whom have also completed their Data Collection Site (DCS) visit (i.e., are enrolled). We are on target to recruit and assess the remaining 10,000 participants by the spring of 2015 given our 60% conversion rate from "pre-recruit" (we currently have a bank of 20,000 pre-recruits) to "recruit". We have obtained health card numbers from over 90% of participants along with their written consent to conduct linkage studies using provincial healthcare administrative databases. Of the participants recruited into the CLSA Comprehensive, we have obtained blood and urine samples from about 94%.

The CLSA is a unique resource ideally positioned for novel contributions to the understanding of the processes of aging including factors associated with longevity and the etiology of diseases and disability. With continued follow-up, repeat collection of the baseline data and biospecimens, linkage to administrative health databases, and the addition of collection tools to incorporate new and emerging areas of science, the CLSA is positioned to be the largest and most complete cohort of aging in Canada. Its value as an important resource for cross-province and population comparisons to inform practice and policy will increase over time, providing research opportunities unprecedented in Canada, and internationally.

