Estimation of sample size requires information on the specific effect sizes that are desired to be detected and/or the desired precision for parameter estimation. Given the diversity of goals and statistical models that are bound to accompany them, it is virtually impossible to provide global meaningful effect sizes for sample size calculations. In addition, the use of the CLSA as a platform for future (and yet unknown) research questions asked and analyzed by others precludes such calculations. Consequently, one strategy we used was to carry out simulations based on simplified hypothesized evolutions of the cohort experience over time. The prevalence of selected exposures and the incidence of selected outcomes, such as particular chronic diseases, over the period of follow-up, were used as a guide to assess the *adequacy* of the proposed sample size in selected situations. First, the expected number of cases of an outcome was simulated for each 3-year wave of the CLSA based on sex- and agespecific incidence rates and taking into account the aging of the cohort over time.²⁷ The simulations also accounted for mortality (based on age and sex specific annual mortality rates from Statistics Canada) and attrition due to loss to follow-up (estimated at 0.5% per year based on the attrition rates for the NPHS (1994-95 to 2000-01).²⁸ For a condition with a high annual incidence rate, such as hypertension (sex- and age-specific incidence rates ranging from 31 to 43 cases/1,000 persons per year),²⁹ we would expect almost 1,520 cases from a cohort of 20,000 people and 1,860 to 2,580 cases from a cohort of

[name] Canadian Longitudinal Study on Aging (CLSA)

Research Proposal

30,000 people (at the end of baseline data collection). We also investigated power profiles for the CLSA for two types of outcomes: hazard ratios (for incidence studies) and odds ratios (for nested case-control studies) based on an iterative simulation-based approach. Simulations were undertaken to determine the minimum detectable hazard ratio (MDHR) for the comprehensive cohort (n=30,000) and for the minimal detectable odds ratio (MDOR) for the combined cohort (n=50,000). (Appendix 3 & 4)

Development of the Content for the Baseline CLSA

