At baseline, as noted, in order to be considered enrolled, a participant must have provided signed consent and completed the baseline assessment. For the CLSA Tracking participants, this is the telephone interview; for the CLSA Comprehensive participants this is the in-home interview and the DCS visit. Technically, a participant cannot withdraw until they have been enrolled, and thus, the Maintaining Contact interview is the first point of contact *initiated by the CLSA* at which withdrawal may be initiated (it can also be initiated by the participant at any point beyond baseline). At the time of writing, 4% of 4,000 CLSA Tracking participants withdrew when contacted to complete the MCQ. **Losses to follow-up**

A protocol for tracing study participants who are not located at follow-up will cover linkages with mortality databases and contact with alternate contacts identified at baseline. At each follow-up, some CLSA participants will have died, and we will make every effort to avoid upsetting family members with uninformed calls. The Clinical Working Group has developed a decedent questionnaire that will be used to obtain information in the time leading up to death from a close family member.

Ongoing Coordinated Ethics Review

The ethics amendments for 2013-2014 were recently submitted and are under review by the McMaster REB, in preparation for posting on the portal for the local REBs to access. During the period of the first follow-up, we will continue to work with the McMaster REB to streamline the coordinated ethics process, and ensure that the local REBs remain committed to the process. We will work closely to support the University of Calgary REB, to bring Calgary into the coordinated process. It has been our experience that many REBs across Canada are under-resourced, and while the portal is an efficient solution for the CLSA, the volume of material to review that the CLSA produces has put a strain on the limited resources at some REBs. Indeed not all REBs have moved to electronic submissions requiring a paper copy of the documents (sometimes as many as 900 pages). As the study progresses and the

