Over the period spanning the second follow-up, we anticipate losses to the cohort of 8 to 10% at the main follow-up and 4 to 5% at the MCQ since last follow-up because of deaths, withdrawals, and losses to follow-up. These figures are based on our current experience with the baseline MCQ and the experience of other cohorts like NPHS in Canada.²⁸ Similar to first follow-up, retention strategies will be employed to keep the withdrawals and losses to a minimum. Ongoing monitoring will be in place to assess projected versus actual attrition over time and the impact on event numbers for key outcomes. Patterns and reasons for attrition of participants will also be assessed, as attrition for systematic reasons may result in subsequent data collection phases becoming increasingly based on nonrandom samples. In the event that the numbers deviate substantially from initial projections or demonstrate evidence of excessive bias, the methodological working group will consider statistical strategies for managing addressing bias and strategies for maintaining study numbers, including consideration of the replenishment of losses, or the introduction of a panel design. Recommendations to alter the study design will be assessed by the SMT and the International Scientific Advisory Committee, and will be presented for approval at the CIHR interim review of the study. Attrition will also have an impact on site budgets and staffing, and will likely result in procedural changes to reflect the decreased number of study participants under observation. For example, it may mean reduced hours of operation and a greater reliance on part time staff. It is conceivable, though, that increasing disability amongst some participants may result in longer DCS visits and longer in-home interviews to maximize data collection (as long as these are acceptable to participants). Ongoing monitoring of methodological and procedural aspects of the study will allow for timely intervention as required.

Adaptations, Accommodations

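### The 0.5% per year loss rate in the sample-size simulations conflicts with the protocol's own refusal and attrition figures, so simulated event numbers are somewhat optimistic

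*Protocol*

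**What the plan says.** The Sample Size Calculations section states that "the expected number of cases of an outcome was simulated for each 3-year wave of the CLSA". On losses it says "The simulations also accounted for mortality (based on age and sex specific annual mortality rates from Statistics Canada") and adds "attrition due to loss to follow-up (estimated at 0.5% per year based on the attrition rates for the NPHS", 1994-95 to 2000-01, reference 28). It does not mention refusals. It then describes simulations of a minimum detectable hazard ratio (MDHR) for the 30,000 Comprehensive participants and a minimum detectable odds ratio (MDOR) for all 50,000, with details in Appendices 3 and 4. The text at hand gives no MDHR or MDOR value.

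Four other places bear on the same quantity:

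- **Aim of the Renewal Application:** "4,000 participants have completed the MCO with a retention rate of approximately 95% (4% have refused to continue and 1% have died").
- **Participant Withdrawal (Aim 3):** "4% of 4,000 CLSA Tracking participants withdrew when contacted to complete the MCQ". The section on developing the baseline content places this contact 18 months after baseline.
- **Aim 4, attrition paragraph:** "we anticipate losses to the cohort of 8 to 10% at the main follow-up and 4 to 5% at the MCQ since last follow-up", covering deaths, withdrawals and losses together. It cites the MCQ experience and again reference 28.
- **Decedents in the CLSA (Aim 3):** 1,117 male and 921 female deaths are projected by Follow-up 1, and a further 1,283 and 1,101 by Follow-up 2.

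**The concern.** The simulations and the Aim 4 plan both rest on reference 28 but carry different non-death loss rates. The only observed figure, from the MCQ, is well above the rate that was simulated. The section headed Attrition Due to Deaths, Refusals to Continue, Losses to Follow-up treats the three as separate components, while the simulation text names only mortality and loss to follow-up. If refusals lie outside the 0.5%, the largest loss observed so far has no stated place in the simulations. If they lie inside it, refusals alone have already exceeded the whole allowance.

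Expected event numbers are at stake, as is any MDHR or MDOR that used the same rate. So is the Aim 4 commitment to compare actual with projected attrition and to consider replenishment or a panel design if they diverge. That comparison needs a single projection.

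**Working it through.** **1. The printed case counts.** The inputs are "sex- and age-specific incidence rates ranging from 31 to 43 cases/1,000 persons per year" and "we would expect almost 1,520 cases from a cohort of 20,000 people and 1,860 to 2,580 cases from a cohort of" 30,000.

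- 30,000 × 0.031 × 2 years = 1,860 and 30,000 × 0.043 × 2 = 2,580, both exact.
- 20,000 × 0.038 × 2 = 1,520, exact, with the rate of 0.038 back-solved.
- 20,000 × 0.031 × 3 = 1,860 and 20,000 × 0.043 × 3 = 2,580 are also exact. On a 3-year basis, however, 1,520 cases from 20,000 would need 25.3 per 1,000, outside the stated range, so the 2-year reading fits better.

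Every exact reproduction contains no mortality and no loss. For 30,000 people over a 3-year wave, with mortality of 1.39% per year (from 2,038 deaths in 50,000), 0.5% loss and cases leaving the risk set, the result is 2,591 to 3,532. The printed counts therefore show no trace of the stated attrition.

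**2. Against the MCQ.** Predicted non-death loss over 18 months is 0.5% × 1.5 = 0.75%. Observed refusal is 4%, about five times as much, or 4%/1.5 = 2.7% per year. Tracking recruitment began in 2011 and the MCQ in autumn 2013 or early 2014, so the true interval may have been longer. At 2 years the rate is 2.0% per year and at 3 years 1.3%, both still above 0.5%.

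**3. Against Aim 4.**

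- Deaths to Follow-up 1: 1,117 + 921 = 2,038, leaving 50,000 − 2,038 = 47,962.
- Deaths from Follow-up 1 to Follow-up 2: 1,283 + 1,101 = 2,384, and 2,384/47,962 = 4.97%.
- Implied non-death loss: (8% − 4.97%)/3 = 1.01% per year to (10% − 4.97%)/3 = 1.68% per year.
- Denominators of 45,000 to 50,000 widen this only to 0.90 to 1.74%.
- In the other direction, 0.5% × 3 + 4.97% = 6.5% per wave, against the 8 to 10% planned.

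**4. Effect on events.** Expected events are N × i × ∫ S(t)·exp(−λt)·exp(−it) dt, where i is incidence, λ is non-death loss and S(t) is survival. S(t) extrapolates the projected deaths in two ways: the hazard is held at its Follow-up 2 level, or it grows by a factor of 1.225 per wave. Assumed incidences are 1, 5 and 37 per 1,000 per year. Events relative to λ = 0.5%:

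| λ per year | 3 years | 6 years | 20 years |
|---|---|---|---|
| 1.0% | 0.993 | 0.985–0.986 | 0.955–0.962 |
| 1.7% | 0.982–0.983 | 0.966–0.967 | 0.897–0.912 |
| 2.7% | 0.968–0.969 | 0.938–0.940 | 0.822–0.847 |

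**5. Effect on the MDHR.** By the Schoenfeld formula, log(MDHR) is proportional to 1/√events.

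- At 20 years and 1.0 to 1.7%, it rises from 1/√0.962 = 1.020 to 1/√0.897 = 1.056, that is by 2 to 6%.
- At 6 years, the largest rise is 1/√0.966 = 1.017.

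As an illustration, assume a two-sided 5% level, 80% power, 10% exposed, n = 30,000 and 20 years. At 5 per 1,000 per year, an MDHR of 1.21–1.22 becomes 1.22–1.23. At 1 per 1,000, 1.53–1.54 becomes 1.54–1.58.

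**The case against.** The strongest reply is that little turns on this. The protocol presents the simulations as simplified and only a guide to adequacy. Tracking recruitment is complete, Aim 4 already plans to monitor attrition and event numbers, and withdrawing participants may allow linkage to continue. Most of this stands and limits the size of the point. Two parts give less comfort. Monitoring needs one agreed projection, and the documents contain two. Continued linkage depends on the participant's choice, and the disease algorithms also use data collection site questions and some tests that stop at withdrawal.

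A reader might also infer more than the documents support:

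- **That refusals were left out.** The text is silent. The 0.5% is said to rest on survey attrition rates, which may include refusals.
- **That the MDHR and MDOR are shown to be wrong.** The 0.5% is described for the case-count simulation. Its use in the power simulations is likely but not stated, and no value is printed.
- **That the printed case counts are inflated by low attrition.** They contain no visible attrition. Even with 2.7% loss, a 3-year calculation for 30,000 gives 2,510 to 3,422, above the printed range.
- **That the MCQ rate should be the main input for 20 years.** It comes from one first contact in 4,000 Tracking participants, while the MDHR concerns the Comprehensive cohort. At 1.6 to 2.7% per year (4% over 2.5 or 1.5 years), adding 4.97% deaths gives 9.8 to 13.1% per wave, mostly above the Aim 4 range.
- **That the mortality input should be lowered because only 1% had died.** That is a rounded figure from fieldwork still in progress.

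**Conclusion.** The inconsistency is real and follows from the protocol's own numbers. A non-death loss of 0.5% per year cannot be squared with 4% refusal at the first contact, or with 8 to 10% total loss per wave once 4.97% deaths are removed. On either reading of what the 0.5% covers, it is too low or incomplete.

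The consequence is small: about 1 to 3% fewer events at 6 years, the span of the two waves in this application, and 4 to 10% fewer at 20 years. Log(MDHR) rises by at most 5 to 6%. For the MDHR and MDOR this holds in direction only, and only if those runs used the 0.5%.

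The result assumes that the projected deaths are right, that the 4 to 5% at the MCQ is part of the 8 to 10% (the natural reading, being half the loss at half the interval), and that withdrawal ends outcome data. The statement that about half the sample will remain at 20 years does not settle the rate. With the two mortality extrapolations, 0.5% leaves 53 to 65% and 1.0 to 1.7% leaves 42 to 59%. This is a minor to moderate point.

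**What to change.** 1. State in Sample Size Calculations whether the 0.5% includes refusals, and whether the MDHR and MDOR simulations used it.
2. Re-run the case-count simulation and those of Appendices 3 and 4 with a combined refusal-plus-loss rate of 1.0 to 1.7% per year as the main input, consistent with Aim 4. Add 2.7% per year as an upper sensitivity case.
3. Restate the expected cases with their follow-up time and cohort, and restate the MDHR and MDOR.
4. Use the same projection as the benchmark for the attrition monitoring in Aim 4, and say there that the MCQ percentage is part of the main-wave percentage, if that is meant.

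The cost is a re-run of existing simulations and a few sentences. Neither the design nor data collection changes. The stated detectable effects become slightly less favourable.

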Epilepsy: In Canada, very little is known about the incidence or prevalence of epilepsy. The national point prevalence, was estimated to be between 5.2 and 5.6 per 1,000, based upon analyses of the 3rd cycle of the National Population Health Survey and the first cycle of the Canadian Community Health Survey, both of which relied upon a single self-report question.¹⁷³ At baseline, the CLSA relied upon a similar single questionnaire item. A recent prospective population-based study demonstrated that the sensitivity of a single self-report questions is only 76.2%.¹⁷⁴ Over the past two years we developed the Canadian Longitudinal Study on Aging – Epilepsy Algorithm (CLSA-EA) and conducted a validation study within the CLSA to estimate the diagnostic accuracy of the CLSA-EA. We administered the CLSA-EA to a consecutive sample of 201 CLSA Comprehensive participants as well as a consecutive sample of 41 individuals from an epilepsy-enriched general neurology clinic. Of the 112 English and 130 French-speaking participants, 34 had a lifetime history of epilepsy. The estimated sensitivity and specificity of the CLSA-EA was 97.1% and 60.6% respectively for the lifetime prevalence of epilepsy; 90.9% and 73.2% for the point prevalence of active epilepsy. In addition, using an *a priori* modified CLSA-EA (i.e., using a more inclusive definition of "probable epilepsy") sensitivities and specificities for the lifetime prevalence of epilepsy were 97.1% and 98.1% and for point prevalence of active epilepsy were 100% and 98.6%. The CLSA-EA will be added to the follow-up for all 50,000 participants. Included on an ongoing basis, it will permit estimation of the incidence of active epilepsy in Canada.

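### The epilepsy algorithm's own accuracy figures do not support estimating the incidence of active epilepsy from unconfirmed positives, and the version to be used is not named

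*Protocol*

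**What the plan says.** Everything below is in the Protocol, Aim 3, Clinical Working Group, Epilepsy paragraph, unless stated otherwise.

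- Background prevalence: "The national point prevalence, was estimated to be between 5.2 and 5.6 per 1,000", taken from two national surveys that each used one self-report question.
- Baseline instrument: "At baseline, the CLSA relied upon a similar single questionnaire item". For such an item the paragraph cites an outside study in which "the sensitivity of a single self-report questions is only 76.2" per cent.
- Validation sample: "a consecutive sample of 201 CLSA Comprehensive participants as well as a consecutive sample of 41 individuals from an epilepsy-enriched general neurology clinic". By language this splits into 112 people (English) and 130 people (French); 34 people in all had ever had epilepsy.
- Accuracy for active epilepsy, CLSA-EA as first described: "90.9% and 73.2% for the point prevalence of active epilepsy". For the modified version, sensitivity and specificity "for point prevalence of active epilepsy were 100% and 98.6" per cent. For lifetime epilepsy the pairs are 97.1% and 60.6% (unmodified), and 97.1% and 98.1% (modified). The modified version is described as the one with the wider definition of a probable case.
- Use: the CLSA-EA goes to all 50,000 at follow-up, without naming a version, and "Included on an ongoing basis, it will permit estimation of the incidence of active epilepsy in Canada".

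The paragraph gives no predictive value, no interval for specificity and no step to confirm positives. Aim 1, Secondary (Passive) Data Collection, plans linkage that would among other things ascertain diagnoses, but does not connect it to CLSA-EA positives.

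**The concern.** A screening instrument applied to a rare condition is governed by its false-positive rate. At 98.6% specificity that rate is 1.4%, about 2.6 times the quoted prevalence (1.4 / 0.54). Most positives would then be people without active epilepsy, and a count of new positives would largely reflect that error.

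Two further features add to this. The version is left open between 98.6% and 73.2% specificity. The instrument also changes from a single item at baseline to the CLSA-EA at Follow-up 1, so prevalent cases missed at baseline could surface as new ones. At stake is a national incidence figure that the protocol presents as something the cohort will be able to deliver. A larger sample does not remove misclassification error.

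**Working it through.** **Inputs** (Epilepsy paragraph): prevalence p = 5.2-5.6 per 1,000, midpoint 5.4; sensitivity (Se) and specificity (Sp) as listed above; validation n = 201 + 41 = 112 + 130 = 242, with 34 lifetime cases; single-item sensitivity 76.2%; 50,000 participants, ignoring attrition.

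**1. Reproducing the stated accuracy.** Lifetime: 33/34 = 97.1%, 126/208 = 60.6%, 204/208 = 98.1%. The number of active cases is not given. Among 1 to 59 active cases, two values fit the percentages: 22 (20/22 = 90.9%, 161/220 = 73.2%, 217/220 = 98.6%) and 33 (30/33, 153/209, 206/209). Both imply 3 false positives for the modified version.

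**2. Share of prevalent positives that are false** = (1-p)(1-Sp) / [p·Se + (1-p)(1-Sp)].
- Modified, p = 0.0054: 0.9946 × 0.014 = 0.01392; 0.01392 / (0.0054 + 0.01392) = 72.1%. At 5.2 per 1,000 it is 72.8%, and at 5.6 it is 71.3%. In 50,000 people this is about 270 true and 696 false positives, an apparent prevalence of 19.3 per 1,000.
- Unmodified, p = 0.0054: 0.9946 × 0.268 = 0.2666; p·Se = 0.0049; false share 98.2%, or about 13,328 false against 245 true.
- At 5.4 per 1,000 and Se 100%, specificity must be about 99.46% for half of positives to be true, and about 99.86% for 80%.

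**3. Precision of the 98.6%.** The exact 95% interval is 96.1-99.7% for 217/220 and 95.9-99.7% for 206/209. The false share at 5.4 per 1,000 then runs from 34% to 88%. The non-cases include clinic patients, and the text does not separate them. In the most favourable split, none of the 201 cohort members is a false positive. The exact upper limit for their false-positive rate is then still 1 - 0.025^(1/201) = 1.8%, over three times the prevalence.

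**4. Higher true prevalence.** If the quoted prevalence is raised for 76.2% sensitivity (5.2/0.762 = 6.8; 5.6/0.762 = 7.3 per 1,000, assuming the single item gives no false positives), the modified version's false share is 65-67%.

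**5. Would statistical correction rescue it?** Corrected prevalence = (apparent + Sp - 1) / (Se + Sp - 1). With apparent prevalence 0.0193 and Se = 1, Sp = 0.961 gives about -2.1% and Sp = 0.997 gives about +1.7%. The standard error of specificity (about 0.8 percentage points) exceeds the prevalence (0.54%).

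**6. Change of instrument.** Cases missed by the baseline item: 50,000 × 0.0052 × 0.238 = 62, and 50,000 × 0.0056 × 0.238 = 67. This takes the quoted prevalence as true and assumes that 76.2% applies to the CLSA item. It affects only a comparison of baseline with Follow-up 1.

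**7. Incident positives.** With new false positives in a fraction f of people per three-year wave and yearly incidence i, the false share is about f / (f + 3i). The protocol gives neither quantity. Assuming i = 0.3-2 per 1,000 and f = 0.3-1.4%, it runs from 0.003/(0.003 + 0.006) = 33% to 0.014/(0.014 + 0.0009) = 94%.

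**8. Description of the modified version.** For lifetime epilepsy, false positives fall from 208 - 126 = 82 to 208 - 204 = 4, while 33 of 34 cases are detected either way. Widening what counts as positive can only add positives, so by itself it cannot raise specificity.

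**The case against.** The strongest reply is that the protocol never says raw positives will be counted as cases, nor that Follow-up 1 will be compared with the baseline item. The claim can fairly be read as referring to successive CLSA-EA waves, which are like with like. Linkage to ascertain diagnoses is already planned, and detailed rules on confirmation and misclassification normally belong in an analysis plan.

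That much stands, and it rules out a stronger reading. A reader might infer that the planned incidence will be too high by some fixed multiple. The documents do not support this: they give no incidence, they do not show whether false positives recur in the same people (and so drop out after the first CLSA-EA wave), and no such comparison is laid down.

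The inputs also have limits. The 1.4% false-positive rate pools cohort members with neurology-clinic patients. The prevalence is national, self-reported and not specific to ages 45-85. The 76.2% comes from another study. The modified definition may be explained in appendices that are not shown.

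The reply does not save the unqualified sentence. The point concerns a positive statement about what the instrument will permit, set beside figures that contradict it unless cases are confirmed. The favourable split in step 3 and the raised prevalence in step 4 do not restore support. The planned linkage is not tied to CLSA-EA positives anywhere in the text.

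**Conclusion.** The concern holds for unconfirmed positives. On the protocol's figures, about 71-73% of prevalent positives on the modified version would be false (34-88% over the interval for specificity; 65-67% with prevalence raised for single-item sensitivity), and about 98% on the unmodified version. These shares assume that the validation specificity carries over to the cohort and that the national prevalence roughly applies. The share among incident positives is not fixed by the documents, so no single fold-error should be quoted.

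Comparing the baseline item with the CLSA-EA at Follow-up 1 would add about 62-67 previously missed cases per 50,000, if 76.2% applies; later waves do not have this problem. It would also go too far to conclude that incidence cannot be estimated. It can be attempted with case confirmation or with a much more precise specificity. The unnamed version and the unexplained rise in specificity are gaps in the text and need clarification; they are not shown to be errors in the algorithm.

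**What to change.** 1. State which CLSA-EA version defines a case, and correct or explain the description of the modified definition so that the rise in specificity at unchanged lifetime sensitivity makes sense.
2. Treat Follow-up 1 as the algorithm's own baseline, and count incidence from Follow-up 2 among people who were algorithm-negative at Follow-up 1.
3. Confirm algorithm positives with the administrative linkage already planned, and with recorded drug identification numbers (DINs) in the Comprehensive arm, where available. Report confirmed cases by arm and linkage status. DINs are recorded only in Comprehensive (Table 2, footnote 2), and drug-plan linkage is limited to those aged 65 or over or on social assistance, where permitted and consented, so confirmation will be uneven.
4. Use misclassification correction only for unconfirmed positives, as a sensitivity analysis with the validation uncertainty carried through. Applying it to cases already confirmed would correct twice.
5. Reword the claim so that estimating incidence is conditional on case confirmation.

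The cost is wording and analysis rules on data already planned. Incidence is reported one wave later, with wider intervals and incomplete confirmation among unlinked participants.
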